# 9.3. Statistical Methods

# 9.3.1. Demographic and Baseline Characteristics

Tabulations of demographic and baseline characteristics will be produced for the efficacy and safety analysis sets.

# 9.3.2. Primary Endpoint(s)

BHV-3000 (rimegepant) 75 mg is tested for superiority to placebo, at a 2-sided alpha level of 0.05, on the primary endpoint of pain freedom at 2 hours post-dose. For rimegepant 25 mg, formal hypothesis testing will not be conducted, and the nominal p-value will be provided only for descriptive purposes.

The endpoint will be evaluated using Mantel-Haenszel risk estimation with stratification by the use of prophylactic migraine medication (yes or no) for the efficacy analysis set. The difference estimate (rimegepant – placebo), 95% CI, and p-value will be reported for each rimegepant treatment group versus placebo. Subjects with missing data at 2 hours post-dose will be imputed to be failure (i.e., Non-completer = Failure; NC=F).

Subjects who use rescue medication at or before the assessment of their primary endpoint will be classified as failures. Sensitivity analyses are described in the Statistical Analysis Plan (SAP).

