After randomization, the subject will be dispensed a single dose of the double-blind study medication that will be taken at the time a migraine attack reaches moderate or severe pain intensity (described below) on the numeric rating scale (NRS) as indicated in the electronic diary (eDiary). The subject will be instructed to take their study medication, as an outpatient, when (if) they have a migraine headache which reaches moderate or severe pain intensity and only after they have identified their most bothersome migraine-associated symptom (phonophobia, photophobia or nausea). The subject will complete an eDiary for up to 48 hours after taking study medication. The subject will contact the study center immediately if they should experience any AEs. Subjects will record efficacy data in their eDiary. This includes the following: onset time of headache, intensity of the headache prior to and at the time of taking study medication. The subject should record all headache intensity leading up to dosing, but should not dose with study medication until the headache reaches moderate or severe pain intensity. Headache severity will be recorded using a 4-point numeric rating scale (no pain, mild pain, moderate pain, severe pain) at the onset of the migraine and after dosing at time points of 15, 30, 45, 60, and 90 minutes and 2, 3, 4, 6, 8, 24 and 48 hours. The presence or absence of associated symptoms (nausea, photophobia, phonophobia) and ratings of functional disability (4-point scale: normal, mildly impaired, severely impaired, requires bedrest) will be recorded at the same time points as the headache severity ratings. Subjects who experience reduction of headache pain to a mild intensity or pain free intensity level will be considered to have achieved pain relief. The subject who does not experience relief of their migraine headache at the end of 2 hours after dosing with study drug (and after the 2-hour assessments have been completed on the eDiary) will be permitted to use the following rescue medication: aspirin, ibuprofen, acetaminophen (up to 2000 mg/day), naproxen (or any other type of nonsteroidal antiinflammatory drug (NSAID)), antiemetics (e.g., metoclopramide), or baclofen. These are the only medications allowed for rescue treatment after 2 hours post dose of study drug. If at the end of 48-hours after dosing with study drug (but before the End of Treatment Visit) subjects are in need of migraine relief, they may take their prescribed standard of care medications, including triptans if not contraindicated, provided all of the assessments have been completed on the eDiary. Exclusionary rescue medication such as opioids, ergotamines, butalbital compounds, and muscle relaxants (except baclofen as a rescue medication, see above) are not allowed during this study. Similarly, if the migraine is relieved by study drug at 2 hours after dosing but then recurs to a moderate or severe intensity level between 2 and 48 hours, the subject will be permitted to take the same rescue therapy as outlined above. In all circumstances, the subject will always continue to complete their eDiary for up to 48 hours after taking the study drug.

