# 9.1. Sample Size

This study will randomize a total of 795 subjects in a 1:1:1 ratio to rimegepant 25 mg, rimegepant 75 mg, or placebo. It is anticipated that this will result in approximately 750 subjects in efficacy analysis set, with roughly 250 subjects in each treatment arm.

Although testing strategy is changed in Protocol version 4.0 and formal hypothesis testing will no longer be conducted for rimegepant 25 mg, the original sample size will remain as it is. The sample size for this study was designed to provide 80% power to test each of the 2 rimegepant doses against placebo at a Bonferroni corrected 2-sided alpha level of 0.025 using a chi-square test. The sample size estimate is based on historical data from pivotal study BHV3000-303, in which the rates of pain freedom were 10.9% for placebo and 21.2% for Rimegepant.

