# 9.2. Analysis Set

The following analysis sets will be used for statistical analyses, as applicable:

- Enrolled: Subjects who sign an ICF and are assigned a subject identification number.
- Full: Subjects in the enrolled analysis set who receive a randomization treatment assignment from the IWRS (rimegepant 25 mg, 75 mg or placebo).
- Safety: Subjects in the enrolled analysis set who take study therapy (rimegepant 25 mg, rimegepant 75 mg, or placebo).
- Efficacy: Subjects in the full analysis set who are randomized only once, take study therapy, have a migraine of moderate or severe pain intensity at the time of treatment, and provide at least one post-dose efficacy data point.

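### The primary analysis is valid, but it does not use pain intensity at dosing (moderate or severe), a pre-treatment value known for everyone in the efficacy set; adding it would bring a small, optional gain

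*Protocol*

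**What the plan says.** Protocol 9.3.2 gives the single formal primary test. Rimegepant 75 mg "is tested for superiority to placebo, at a 2-sided alpha level of 0.05", and the endpoint is "evaluated using Mantel-Haenszel risk estimation with stratification by the use of prophylactic migraine medication (yes or no" in the efficacy analysis set. Randomization (Protocol 7.2.1) is stratified by the same factor alone.

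Pain before dosing is collected. The Synopsis (Overall Design) lists among the eDiary items the "intensity of the headache prior to and at the time of taking study medication". Table 1, footnote 2, makes completion of the pre-dose eDiary questions a condition for taking study drug. Protocol 9.2 admits to the efficacy set only subjects who "have a migraine of moderate or severe pain intensity at the time of treatment". Every subject in the primary analysis therefore has a known value, moderate or severe.

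No section of the protocol uses that value as a stratum or covariate. Section 9.3.2 refers sensitivity analyses to the SAP. The SAP supplied belongs to another study (C4951021, migraine prevention; its Section 1) and does not cover this endpoint.

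**The concern.** The endpoint is a score of none at 2 hours on the four-point pain scale. A subject who doses at severe has further to fall than one who doses at moderate, so intensity at dosing is a natural candidate predictor. It is measured before treatment under double-blind conditions, so treatment cannot affect it.

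If it does predict outcome, omitting it has two effects. Some outcome variance that could be removed stays in the standard error. A chance difference between arms in the share of severe attacks also carries into the estimated treatment difference. If such an imbalance appeared after unblinding, any adjustment for it on the only formal primary test would be post hoc.

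The same statistics apply to the secondary endpoints (Protocol 9.3.3), which are tested in a fixed sequence that stops at the first failure (9.3.4). Pain relief at 2 hours is first in that sequence and uses the same pain scale.

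**Working it through.** **Inputs from Protocol 9.1 and 9.3.2.** The sample size was "designed to provide 80% power to test each of the 2 rimegepant doses against placebo at a Bonferroni corrected 2-sided alpha level of 0.025"; "the rates of pain freedom were 10.9% for placebo and 21.2% for Rimegepant"; "approximately 750 subjects in efficacy analysis set, with roughly 250 subjects in each treatment arm". The current test uses two-sided alpha 0.05.

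**The plan's own figure.** Let p0 = 0.109, p1 = 0.212, d = 0.103, n = 250 per arm and mean rate p̄ = 0.1605. Power = Φ{[d√n − z√(2p̄(1−p̄))] / √V}, where V = 0.109×0.891 + 0.212×0.788 = 0.2642.
- At alpha 0.025, power is 81.7%, which agrees with the stated 80%.
- At the current alpha of 0.05, it is 88.3%.
- The unpooled standard error is √(0.2642/250) = 3.25 points; using it for the test gives 88.7%.

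**Assumptions not in the documents.** The severe share q is 20-50%. The odds ratio (OR) for pain freedom, severe versus moderate, is 0.3 to 1.0 and the same in both arms. The overall rates stay at 10.9% and 21.2%. The prophylaxis split is left out because no share is given.

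**Formulas.** With moderate-stratum rates a0, a1 and severe-stratum rates b0, b1, the within-stratum variance is Vs = (1−q)[a0(1−a0) + a1(1−a1)] + q[b0(1−b0) + b1(1−b1)]. The variance reduction is 1 − Vs/V. For power, the pooled term is also computed within strata. The SD of the between-arm difference in severe share is √(2q(1−q)/n). The shift at 1.96 SD is 1.96 × that SD × the mean over arms of (a − b).

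**Worked extreme (q = 0.5, OR = 0.3).**
- Placebo rates are 16.29% moderate and 5.51% severe (mean 10.90%). Active rates are 30.68% and 11.72% (mean 21.20%).
- Vs = 0.5(0.1364 + 0.2127) + 0.5(0.0521 + 0.1035) = 0.2523, so the reduction is 1 − 0.2523/0.2642 = 4.5%.
- Power goes from 88.3% to 89.6%, a gain of 1.3 points. The equivalent sample is 250 × (0.2642/0.2523 − 1), about 12 per arm.
- The imbalance SD is √(0.5/250) = 4.47 points, and 1.96 SD is 8.77 points. The mean rate gap is (10.78 + 18.96)/2 = 14.87 points. The shift is 0.0877 × 0.1487 = 1.3 points, or 0.40 of the 3.25-point standard error.

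**Range over q = 20-50%.**

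| OR | Variance reduction | Power (from 88.3%) | Shift at 1.96 SD, points |
|---|---|---|---|
| 1.0 | 0 | no change | 0 |
| 0.7 | 0.3-0.4% | 88.4% | 0.3-0.4 |
| 0.5 | 0.8-1.6% | 88.5-88.8% | 0.6-0.8 |
| 0.3 | 1.9-4.5% | 88.8-89.6% | 0.8-1.3 |

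**Simulation (200,000 trials per scenario, OR 0.33 to 1.0).** Type I error was about 0.051-0.053 without the intensity stratum and 0.050-0.052 with it. With OR 1.0, the SD of the estimate rose by only 0.003-0.004 points (for example 3.247 to 3.251), so an uninformative stratum costs almost nothing.

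**The case against.** The strongest reply is that nothing is wrong with the plan. It analyses by the factor used at randomization, its type I error is close to nominal, and power is already about 88% because the sample size was kept when alpha moved from 0.025 to 0.05. The prognostic value of intensity is nowhere documented, and with no association the gain is zero. A 1.3-point shift is ordinary sampling variation that the planned confidence interval already covers. All of this stands, and it is why the point is optional.

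Three stronger readings might be inferred, and the documents support none of them.
- *The omission biases the primary result.* It does not. Chance imbalance averages out over randomizations and is a matter of precision and interpretation.
- *Randomization should have been stratified by intensity.* It could not have been: subjects are randomized at the Baseline Visit and take the drug home for up to 45 days (Protocol 4.3.2), so the treated attack has not yet occurred.
- *The trial has no severity-adjusted analysis at all.* This cannot be said without this study's SAP. Protocol 9.3.2 does, however, fix the primary method without the variable.

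Two limits on scope also stand. Completeness is guaranteed for the efficacy set, not for every treated subject. And because intensity may be recorded more than once before dosing, the stratum needs a stated rule.

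**Conclusion.** The point holds as a low-priority improvement, not as an error. The primary analysis leaves out a pre-treatment value that is complete in its own analysis set. With 10.9% versus 21.2%, 250 per arm and two-sided alpha 0.05, including it would cut the variance by 0 to about 4.5%, add 0 to about 1.3 points of power, and remove a shift of 0 to 1.3 points (against a planned 10.3) at a 1.96-SD imbalance. Where the truth lies in those ranges depends on the severe share and the odds ratio, both assumed here. The case for acting is that the cost is small if the factor proves uninformative, and that only prespecification makes the adjustment credible. The planned test remains valid if nothing is changed.

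**What to change.** Before unblinding, prespecify the Mantel-Haenszel risk difference stratified by prophylactic medication use (yes, no) and the last eDiary pain intensity recorded before dosing (moderate, severe), for the primary endpoint and for pain relief at 2 hours. Keep the two-stratum analysis as supportive. If the four strata are extended to secondary endpoints assessed only in a subset (for example, subjects with nausea at dosing), state in advance that the analysis reverts to two strata when a stratum is sparse, and define sparse.

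The cost is four strata in place of two, plus a written amendment with IRB/IEC approval (Protocol 12) and matching SAP text. No new data are collected. First check this study's own SAP for an intensity-adjusted analysis; if there is one, the change is mainly which analysis is named as primary.

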# 9.3.3. Secondary Endpoint(s)

The same statistics for secondary endpoints (as listed in Section 3.2) will be presented as those for the primary endpoint.

For endpoints based on a single time point, such as pain freedom at 2 hours post-dose, subjects with missing data at a single time point will be classified as failures (NC=F). For endpoints based on multiple time points, such as sustained pain relief from 2 to 48 hours post-dose, subjects with missing data at (1) 2, 24, or 48 hours post-dose, or (2) more than 1 time point from 3 to 8 hours post-dose will also be classified as failures.

For all secondary endpoints except the rescue medication use within 24 hours post-dose, subjects who use rescue medication at or before the assessment of their endpoint will be classified as failures.

See section 9.3.5 for safety endpoints.

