### 2.2. Secondary Objective(s)

- To compare the efficacy of rimegepant 75 mg with placebo in the acute treatment of migraine in Japanese subjects on the following secondary endpoints:
  - Pain relief at 2 hours post-dose
  - Freedom from the MBS associated with migraine at 2 hours post-dose
  - The ability to function normally at 2 hours post-dose
  - Sustained pain relief from 2 to 24 hours post-dose
  - Rescue medication use within 24 hours of initial treatment
  - Sustained pain relief from 2 to 48 hours post-dose
  - Freedom from photophobia at 2 hours post-dose
  - Sustained pain freedom from 2 to 24 hours post-dose
  - Freedom from phonophobia at 2 hours post-dose
  - Sustained pain freedom from 2 to 48 hours post-dose
  - Freedom from nausea at 2 hours post-dose
  - Pain relapse from 2 to 48 hours post-dose
- To compare the efficacy of rimegepant 25 mg with placebo in the acute treatment of migraine in Japanese subjects on the same efficacy endpoints
- To evaluate the tolerability and safety of rimegepant 75 mg and 25 mg in the acute treatment of migraine

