#### 3.2. Secondary Endpoint(s)

- Pain relief at 2 hours post-dose will be assessed using the percentage of subjects that report a pain intensity level of none or mild at 2 hours post-dose.
- Freedom from the MBS at 2 hours post-dose will be assessed using the percentage of subjects with an MBS reported before dosing that is absent at 2 hours post-dose. The MBS before dosing will be reported as nausea, phonophobia, or photophobia. Symptom status will be reported post-dose as present or absent for each symptom (nausea, phonophobia, and photophobia).
- Ability to function normally at 2 hours post-dose will be assessed using the percentage of subjects with a functional disability level of normal at 2 hours post-dose in the subset of subjects with functional disability at the time of dosing. Functional disability level will be measured on a 4-point numeric rating scale (0=normal, 1=mildly impaired, 2=severely impaired, 3=requires bedrest), and functional disability will be defined as mildly impaired, severely impaired, or requires bedrest.
- Sustained pain relief from 2 to 24 hours post-dose will be assessed using the percentage of subjects with pain intensities of none or mild from 2 to 24 hours post-dose.
- Rescue medication use within 24 hours post-dose will be assessed using the percentage of subjects that take rescue medication within 24 hours after administration of study medication (rimegepant or placebo).
- Sustained pain relief from 2 to 48 hours post-dose will be assessed using the percentage of subjects with pain intensities of none or mild at all time points from 2 to 48 hours post-dose.
- Freedom from photophobia at 2 hours post-dose will be assessed using the percentage of subjects with photophobia absent at 2 hours post-dose in the subset of subjects with photophobia present at the time of dosing.
- Sustained pain freedom from 2 to 24 hours post-dose will be assessed using the percentage of subjects with pain intensities of none at all time points from 2 to 24 hours post-dose.

- Freedom from phonophobia at 2 hours post-dose will be assessed using the percentage of subjects with phonophobia absent at 2 hours post-dose in the subset of subjects with phonophobia present at the time of dosing.
- Sustained pain freedom from 2 to 48 hours post-dose will be assessed using the percentage of subjects with pain intensities of none at all time points from 2 to 48 hours post-dose.

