# 9. STATISTICS

Complete details on the statistical methods for this study may be found in the Statistical Analysis Plan (SAP).

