# 9.3.4. Multiplicity Correction

For rimegepant 75 mg, if the primary endpoint test is significant, then the secondary endpoints will be evaluated using a hierarchical gate-keeping procedure, with each test in the hierarchy conducted at alpha=0.05. Testing will stop at the first non-significant endpoint. Nominal p-value will still be reported but will not be used for inference purpose.

These secondary endpoints will be tested in the order shown in the Study Objectives section of this protocol.

For rimegepant 25 mg, formal hypothesis testing will not be conducted, and the nominal p-values will be presented only for descriptive purposes as described in Section 9.3.2.

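### As literally worded, the Protocol 9.3.3 missing-data rule makes a missing 48-hour entry a failure on the two endpoints that end at 24 hours: a minor wording gap, probably unintended

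*Protocol*

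**What the plan says.** Protocol 9.3.3 has two missing-data sentences. The first covers endpoints read at one time point. The second covers endpoints based on multiple time points and gives sustained pain relief from 2 to 48 hours only as an example. Under the second, failures are "subjects with missing data at (1) 2, 24, or 48 hours post-dose", plus subjects with more than one missing entry from 3 to 8 hours.

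Two multi-time-point endpoints in Protocol 3.2 end at 24 hours. Sustained pain relief requires "pain intensities of none or mild from 2 to 24 hours post-dose". Sustained pain freedom requires "pain intensities of none at all time points from 2 to 24 hours post-dose".

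The rescue rule in 9.3.3 is tied to each endpoint: "subjects who use rescue medication at or before the assessment of their endpoint will be classified as failures". The missing-data rule has no such tie.

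Protocol 9.3.4 tests the secondary endpoints for 75 mg in the order of the Study Objectives section, each at alpha 0.05, and "Testing will stop at the first non-significant endpoint". In the Protocol 2.2 list, sustained pain relief from 2 to 24 hours is fourth and "Sustained pain freedom from 2 to 24 hours post-dose" is eighth of twelve efficacy endpoints.

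Protocol 9 leaves full statistical detail to the SAP. The SAP supplied is, by its Section 1, for C4951021, a migraine prevention study, and does not define these endpoints.

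**The concern.** The endpoint definition and the missing-data rule can classify the same subject differently. A subject with complete entries and a sustained response through 24 hours meets Protocol 3.2. If only the 48-hour entry is absent, the literal text of 9.3.3 makes that subject a failure because of a time point outside the endpoint.

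Both endpoints are formally tested for 75 mg. The fourth gates the fifth (rescue medication use within 24 hours) and the eighth gates the ninth (freedom from phonophobia), so a diluted difference at either could end formal testing early. Two programmers could also derive different results from the same sentence, which a prespecified rule should prevent.

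**Working it through.** **Which subjects are affected.** From 2 hours on, the diary times in Protocol 4.3.2.1 are 2, 3, 4, 6, 8, 24 and 48 hours, giving 2^7 = 128 patterns of missing entries. For an endpoint ending at 24 hours, compare:

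- Literal rule: failure if 2, 24 or 48 h is missing, or more than one of 3, 4, 6, 8 h.
- Window-limited rule: failure if 2 or 24 h is missing, or more than one of 3, 4, 6, 8 h.

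They differ only when 48 h is missing, 2 h and 24 h are present, and at most one of the four entries from 3 to 8 h is missing: 1 + 4 = 5 patterns.

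**Which endpoints are affected.** The primary endpoint and secondary endpoints 1, 2, 3, 7, 9 and 11 are 2-hour measures. Endpoints 6, 10 and 12 (sustained pain relief, sustained pain freedom and pain relapse, each to 48 hours) include the 48-hour entry in their window. Endpoint 5, rescue use, comes from a paper diary (Protocol 6.3.3), not the timed entries. That leaves endpoints 4 and 8.

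**Reproducing the plan's figure.** Protocol 9.1 gives about 250 evaluable subjects per arm and says "the rates of pain freedom were 10.9% for placebo and 21.2% for Rimegepant", with 80% power at two-sided alpha 0.025. For two proportions:

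- s0 = sqrt(2·p̄(1−p̄)/n), where p̄ is the mean of the two rates
- s1 = sqrt(p1(1−p1)/n + p2(1−p2)/n)
- power = Φ((|p2−p1| − z·s0)/s1)

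Here s0 = 0.03283, s1 = 0.03251 and z = 2.241, so power = Φ((0.103 − 0.0736)/0.03251) = 81.7%, consistent with the stated 80%. At the current alpha of 0.05 (z = 1.960), power = Φ((0.103 − 0.0643)/0.03251) = 88.3%.

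**Size of the effect (illustrative).** Let m be the share of 24-hour responders, equal in both arms, whose only disqualifying gap is the 48-hour entry. Each rate is then multiplied by (1−m). The documents give neither m nor any sustained-response rate, so all the rates below are assumptions. The first row uses the 2-hour pain-freedom rates as stand-ins. The next two suppose that 75% or 50% of 2-hour pain-free subjects stay pain-free to 24 hours, because sustained pain freedom cannot exceed 2-hour pain freedom. The last uses higher rates, nearer to what a pain-relief endpoint might show.

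| Assumed rates, placebo vs 75 mg | m = 0 | m = 2% | m = 5% | m = 10% |
|---|---|---|---|---|
| 10.9% vs 21.2% | 88.3% | 87.5% | 86.3% | 84.1% |
| the same × 0.75 | 75.8% | 74.8% | 73.3% | 70.7% |
| the same × 0.50 | 56.4% | 55.4% | 54.1% | 51.7% |
| 30% vs 45% | 93.6% | 92.9% | 91.7% | 89.3% |

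Entries are power at n = 250 per arm, two-sided alpha 0.05, unstratified, as an approximation to the planned Mantel-Haenszel analysis. Within each row the loss is about 1 point at m = 2%, 2 to 2.5 at 5%, and 4 to 5 at 10%. In the first row the difference goes from 10.3 points to 10.1, 9.8 and 9.3. At m = 5% the subjects recoded there are 250 × 0.109 × 0.05 = 1.4 of 27 placebo responders and 250 × 0.212 × 0.05 = 2.7 of 53 on 75 mg.

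**The case against.** The literal reading is arguably too strict. The companion sentence on single-time-point endpoints also does not say which time point must be missing, yet nobody would fail a subject on 2-hour pain freedom for a missing 45-minute entry: the endpoint's own time is understood. In the second sentence the example is a 2-to-48-hour endpoint, and the listed times are exactly that endpoint's diary times. On a natural reading, 48 hours drops out for an endpoint ending at 24. The amendment summary also says that the statistical-methods text, including 9.3.3, was clarified and aligned with the study's SAP, which may already be window-specific. Protocol 5.5 requires diary entries through 48 hours in all circumstances, so few subjects may be affected.

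These arguments stand and set the severity. They do not remove the gap: the protocol sentence states no window limit, and the document that might supply one could not be checked.

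Three stronger inferences are not supported:

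- A reader might infer that the trial will misclassify subjects. The documents show only that the wording permits it.
- A reader might infer a biased treatment effect. Equal loss dilutes the difference, which is conservative. Unequal loss could move it either way, as under any rule that counts missing as failure, but the documents give no evidence of it and no basis for a size.
- A reader might take the 75.8% or 56.4% as a consequence of the rule. Those starting values come from the assumed persistence of response. The rule accounts only for the change along each row.

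**Conclusion.** The point holds as a wording gap of minor severity. Taken literally, 9.3.3 fails a subject on two formally tested 2-to-24-hour endpoints for lacking an entry outside their window. The authors probably intended in-window time points only.

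The size is unknown and probably small: about 1 to 5 points of power at each of the two tests if 2% to 10% of 24-hour responders are recoded for the 48-hour gap alone. That range rests on assumed missingness equal in both arms, on assumed response rates, and on an unstratified approximation. Apart from the gating described above, no other endpoint is touched.

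**What to change.** Before unblinding, keep the general rule in 9.3.3 and add a window limit to its first limb. After "subjects with missing data at (1) 2, 24, or 48 hours post-dose", insert: *where that time point falls within the endpoint's window*. The second limb, more than one missing entry from 3 to 8 hours, stays as it is.

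The 48-hour condition then applies only to endpoints that extend to 48 hours. Qualifying the general rule is safer than writing separate rules for the 2-to-24-hour and 2-to-48-hour sustained endpoints, because that would leave pain relapse from 2 to 48 hours, last in the testing order, without a missing-data rule.

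Then confirm that the derivation in the study's own SAP matches. The cost is one clause and one check of a derivation, with no new data.
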